6.5.5 Management of Specific Adverse Events or Adverse Drug Reactions

Based on nonclinical data, the main anticipated toxicity for M8891 may include anemia, neutropenia, leukopenia, thrombocytopenia, opportunistic infections, nausea, diarrhea, gastrointestinal (GI) hemorrhage and osteoporosis (see Section 3.3.1). Cabozantinib safety profile has been established ([Cabometyx USPI 2019](#)).

Potential occurring AEs that study subjects are likely to encounter during the study period and guidance on the management is presented in the Table 12.

Table 12 Management of Specific AEs with M8891 Combined with Cabozantinib

Adverse Event	Management Recommendation ^a
Diarrhea	
Subjects should be instructed to notify their physician immediately at the first signs of poorly formed or loose stool or an increased frequency of bowel movements.Administration of antidiarrheal/ antimotility agents is recommended at the first sign of diarrhea as initial management.Some subjects may require concomitant treatment with more than one antidiarrheal agent. When therapy with antidiarrheal agents does not control the diarrhea to tolerable levels, study treatment should be temporarily interrupted, or dose reduced (Section 5.1.3.5).When the diarrhea is controlled, retreatment with study treatment may be acceptable per Investigator decision.In addition, general supportive measures should be implemented including continuous oral hydration, correction of fluid and electrolyte abnormalities, small frequent meals, and stopping lactose-containing products, high fat meals, and alcohol.
Nausea and Vomiting	
Antiemetic agents are recommended as clinically appropriate at the first sign of nausea and vomiting or as prophylaxis to prevent emesis, along with supportive care according to clinical practice guidelines.In the case of cabozantinib, the 5-HT3 receptor antagonists are recommended over chronic use of NK-1 receptor antagonists and dexamethasone (NK-1 receptor antagonists can induce or inhibit CYP3A4, and glucocorticoids induce CYP3A4 and thus could lower cabozantinib exposure (see Section 7 in cabozantinib USPI (Cabometyx USPI 2019)).For cabozantinib, caution is also recommended with the use of nabilone, which is a weak inhibitor of CYP3A4.
Stomatitis and Mucositis	
Preventive measures may include a comprehensive dental examination to identify any potential complications before study treatment is initiated. Removal of local factors should be instituted as indicated, such as modification of ill-fitting dentures and appropriate care of gingivitis (dental examination/procedures before study initiation will be recommended but not covered by the study).During treatment good oral hygiene and standard local treatments such as nontraumatic cleansing and oral rinses (e.g., with a weak solution of salt and baking soda) should be

Adverse Event	Management Recommendation ^a
	
maintained. The oral cavity should be rinsed and wiped after meals, and dentures should be cleaned and brushed often to remove plaque.
 
 • Local treatment should be instituted at the earliest onset of symptoms. • Obtain bacterial/viral culture if oral infection is suspected and treat infection as indicated by local guidelines. • When stomatitis interferes with adequate nutrition and local therapy is not adequately effective, dose reduction or temporary withholding of study treatment should be considered.
Hepatobiliary Disorders	
 • It is recommended that subjects with elevation of ALT, AST, and/or bilirubin have more frequent laboratory monitoring of these parameters. • If possible, hepatotoxic concomitant medications should be discontinued in subjects who develop increased values of ALT, AST, or bilirubin. • Dose reductions of study treatment should be considered in any subject who develops drug-related Grade 2 elevated ALT, AST, or bilirubin lasting longer than 1 week. • A subject who develops Grade ≥ 3 elevated ALT, AST, or bilirubin should have study treatment held and restarted at a reduced dose (Section 5.1.3.5) after ALT, AST, and bilirubin levels resolve to at least Grade ≤ 1 or baseline. • In subjects with recurrence of drug-related Grade ≥ 3 elevated ALT, AST, or bilirubin at the lowest dose level, study treatment should be discontinued. • In subjects who develop ALT/AST elevations $> 3 \times$ ULN in combination with a bilirubin elevation $> 2 \times$ ULN without reasonable other explanation, drug-induced liver injury should be suspected and study treatment should be interrupted. • Reinstitution of study treatment after recovery of ALT, AST, and bilirubin to Grade 1 or baseline level must be discussed and approved with the Sponsor.
Hematological Disorders	
 • Hematological toxicities (i.e., neutropenia and thrombocytopenia) and associated complications may be managed with dose interruptions and/or dose reductions. Use of granulocyte colony-stimulating factor support for neutrophil recovery is allowed per Investigator discretion and in accordance with accepted guidelines after the first incidence of clinically relevant cytopenia. • Complete blood counts with differentials and platelets should be performed regularly. Subjects with hematologic toxicities may require additional or more frequent laboratory tests according to institutional guidelines. • Febrile neutropenia or evidence of infection associated with neutropenia must be assessed immediately and treated appropriately and in a timely manner according to institutional guidelines. • Dose reductions or dose interruptions for anemia are not mandated but can be applied as clinically indicated. Supportive care such as red blood cell transfusions may be managed according to institutional guidelines.
Fatigue, Anorexia, and Weight Loss	
 • Common causes of fatigue such as anemia, deconditioning, emotional distress (depression and/or anxiety), nutrition, sleep disturbance, and hypothyroidism should be ruled out and/or these causes treated according to standard of care. Individual non-pharmacological and/or pharmacologic interventions directed to the contributing and treatable factors should be given. • Pharmacological management with psychostimulants such as methylphenidate should be considered after disease specific morbidities have been excluded. Note: Chronic use of modafinil should be avoided because of its potential to reduce cabozantinib exposure (see Section 7 in cabozantinib USPI (Cabometyx USPI 2019)). • Dose reduction of study treatment should be considered when general or pharmacological measures have not been successful in reducing symptoms. • Dose interruption may be considered for Grade ≥ 3 fatigue despite optimal management, at the Investigator's discretion. • Anorexia and weight loss should be managed according to local standard of care including nutritional support. Pharmacologic therapy such as megestrol acetate should be considered for appetite enhancement. Should these interventions prove ineffective, dose hold and reductions may be considered for Grade ≥ 3 anorexia or weight loss.
Skin Disorders	
 • All subjects on study should be advised on prophylactic skin care. This includes the use of hypoallergenic moisturizing creams, ointment for dry skin, and sunscreen with sun protection factor ≥ 30, avoidance of exposure of hands and feet to hot water, protection of

Adverse Event	Management Recommendation ^a								
	
pressure sensitive areas of hands and feet, and use of thick cotton gloves and socks to prevent injury and to keep the palms and soles dry.
 
 Subjects with skin disorders should be carefully monitored for signs of infection (e.g., abscess, cellulitis, or impetigo). Early signs of hand-foot syndrome could be tingling, numbness, and slight redness or mild hyperkeratosis. Early manifestations include painful, symmetrical red and swollen areas on the palms and soles. The lateral sides of the fingers or peri-ungual zones may also be affected. Adequate interventions are required to prevent worsening of skin symptoms such as blisters, desquamations, ulcerations, or necrosis of affected areas. Aggressive management of symptoms is recommended, including early dermatology referral. In the case of study treatment-related skin changes (e.g., rash, hand-foot syndrome), the Investigator may request that additional assessments be conducted with the subject's consent. These assessments may include digital photographs of the skin changes and/or a biopsy of the affected skin and may be repeated until the skin changes resolve. VEGF inhibitors can cause wound healing complications and wound dehiscence which may occur even long after a wound has been considered healed. Therefore, surgical and traumatic wounds must have completely healed prior to starting study treatment and be monitored for wound dehiscence or wound infection while the subject is being treated with M8891 with cabozantinib. 								
Hypertension	
 Hypertension is a common class effect of drugs that inhibit VEGF pathways. Blood pressure should be monitored in a constant position at each visit (either sitting or supine). In general, subjects with known hypertension should be optimally managed prior to study entry. Decisions to decrease or hold the dose of study treatment must be based on blood pressure readings taken by a medical professional and must be confirmed with a second measurement at least 5 minutes following the first measurement. Other than for hypertension requiring immediate therapy, the presence of new or worsened hypertension should be confirmed at a second visit before taking therapeutic action. It is recommended that this second visit occurs within 1 week. In the case of hypertensive crisis or hypertensive encephalopathy, study treatment should be discontinued. 								
Thromboembolic Events	
 Study treatment should be discontinued in subjects who develop PE or DVT, an acute myocardial infarction or any other clinically relevant arterial thromboembolic complication (Section 5.5). 								
Proteinuria	
 During each safety assessment visit, proteinuria will be quantified by measuring the urine protein-to-creatinine (UPCR) ratio. In addition, urine dipstick analysis will be performed (see Table 2 and Table 3). 
  
 Severity of Proteinuria (UPCR)	Action To Be Taken	
   
 1 mg/mg (\leq 113.1 mg/mmol)	 
 No change in study treatment or monitoring 	
 
 > 1 and $<$ 3.5 mg/mg ($>$ 113.1 and $<$ 395.9 mg/mmol)	 
 No change in study treatment required Consider confirming with a 24-hour protein assessment within 7 days 	
 
 \geq 3.5 mg/mg (\geq 395.9 mg/mmol)	 
 Repeat UPCR within 7 days and once per week. If UPCR $<$ 1 on 2 consecutive readings, UPCR monitoring can revert to protocol-specific times. (Second reading is confirmatory and can be done within 1 week of first reading.) Hold study treatment pending repeat UPCR within 7 days and/or 24-hour urine protein. If \geq 3.5 on repeat UPCR, continue to hold study treatment and check UPCR every 7 days. If UPCR decreases to $<$ 2, 	
  
	Severity of Proteinuria (UPCR)	Action To Be Taken	1 mg/mg (\leq 113.1 mg/mmol)	
 No change in study treatment or monitoring 	> 1 and $<$ 3.5 mg/mg ($>$ 113.1 and $<$ 395.9 mg/mmol)	
 No change in study treatment required Consider confirming with a 24-hour protein assessment within 7 days 	\geq 3.5 mg/mg (\geq 395.9 mg/mmol)	
 Repeat UPCR within 7 days and once per week. If UPCR $<$ 1 on 2 consecutive readings, UPCR monitoring can revert to protocol-specific times. (Second reading is confirmatory and can be done within 1 week of first reading.) Hold study treatment pending repeat UPCR within 7 days and/or 24-hour urine protein. If \geq 3.5 on repeat UPCR, continue to hold study treatment and check UPCR every 7 days. If UPCR decreases to $<$ 2,
Severity of Proteinuria (UPCR)	Action To Be Taken								
1 mg/mg (\leq 113.1 mg/mmol)	
 No change in study treatment or monitoring 								
> 1 and $<$ 3.5 mg/mg ($>$ 113.1 and $<$ 395.9 mg/mmol)	
 No change in study treatment required Consider confirming with a 24-hour protein assessment within 7 days 								
\geq 3.5 mg/mg (\geq 395.9 mg/mmol)	
 Repeat UPCR within 7 days and once per week. If UPCR $<$ 1 on 2 consecutive readings, UPCR monitoring can revert to protocol-specific times. (Second reading is confirmatory and can be done within 1 week of first reading.) Hold study treatment pending repeat UPCR within 7 days and/or 24-hour urine protein. If \geq 3.5 on repeat UPCR, continue to hold study treatment and check UPCR every 7 days. If UPCR decreases to $<$ 2, 								

Adverse Event	Management Recommendation ^a
	
Nephrotic syndrome
 
 • restart study treatment at a reduced dose and monitoring of urine protein/creatinine should continue weekly until the UPCR decreases to < 1. • Discontinue study treatment
Corrected QTcF interval Prolongation	
If at any time on study the average QTcF interval from the 3 ECGs is > 500 ms, the following actions should be taken:
 
 • Withhold study treatment • Immediately notify the Sponsor • Hospitalize symptomatic subjects (e.g., with palpitations, dizziness, syncope, orthostatic hypotension, a significant ventricular arrhythmia on ECG) for a thorough cardiology evaluation and management • Consider cardiology consultation for asymptomatic subjects for evaluation and management • Check electrolytes, especially magnesium, calcium, and potassium; correct abnormalities as clinically indicated • Check concomitant medications for any medication that may have contributed to QT prolongation, and if possible, discontinue these medications (refer to http://www.qtdrugs.org) • Repeat ECG triplicates hourly until the average QTcF interval is ≤ 500 ms • Subjects with QTcF interval prolongation and symptoms must be monitored closely until the QTcF interval prolongation and symptoms have resolved. 
Study treatment may be restarted at a reduced dose level if ALL the following conditions are met:
 
 • Symptoms are determined to be unrelated to the QT interval prolongation • The QTcF interval value returns to ≤ 500 ms • Study treatment has been interrupted through a minimum of 1 week following the return of the QTcF interval to ≤ 500 ms • QT prolongation can be unequivocally associated with an event other than study treatment administration and is treatable/has been resolved • Sponsor has reviewed all available information and has agreed to the continuation of study treatment 
Following reinitiation of study treatment, ECGs must be repeated weekly for 2 weeks, then every 2 weeks for 1 month, then according to the protocol-defined time points.
 
Study treatment must be permanently discontinued if either of the following applies:
 
 • Cardiac evaluation confirms that symptoms are the consequence of QT interval prolongation • Recurrence of QTcF interval prolongation after reinitiation of study treatment at a reduced dose
Hypophosphatemia	
 • Serum phosphorus should be monitored frequently while receiving study treatment. • Mild hypophosphatemia is usually asymptomatic or symptoms can be non-specific such as weakness, bone pain, rhabdomyolysis, or altered mental status. • Other causes of hypophosphatemia such as poor nutrition, chronic alcoholism, malabsorption, excessive antacid use, glucocorticoids use, kidney dysfunction, respiratory alkalosis, vitamin D deficiency should be ruled out and/or these causes treated according to standard of care. • Mild to moderate hypophosphatemia should be managed by oral replacement including food that are high in phosphate (diary items, meats, beans) and/or oral phosphate supplements according to standard clinical practice guidelines • Clinically relevant hypophosphatemia should be managed according to the dose modification guidelines as outlined in Section 5.1.3.5 or as clinically indicated
Thyroid Disorders	Management of thyroid dysfunction (e.g., symptomatic hypothyroidism) should follow accepted clinical practice guidelines and dose modification guidelines as outlined in Table 10.

^a Subjects with pre-existing conditions who are at greater risk of experiencing serious toxicities should be monitored carefully throughout the study. For cabozantinib, Investigators are encouraged to refer to local product label; dose modification of any study treatment should always be considered in consultation with the Sponsor's Medical Responsible.

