5.1.3.5 Dose Modification

5.1.3.5.1 M8891

In Cycle 1 dose escalation Part 1 and Part 2A, dose modification is not allowed. After completion of the DLT period in subsequent cycles of Part 1 and Part 2A and in all cycles of Part 2B, if Grade \geq 3 non-hematological AEs (for exceptions see 5.1.3.3 Section) or Grade \geq 4 hematological AEs occur but they recover to Grade 1 in \leq 14 days of treatment interruption, and in the absence of disease progression, the subject may continue treatment at a lower dose i.e., 1 level below the current dose or a dose defined by the SMC. If indicated, a further dose reduction is possible.

In Part 1, if a subject does not tolerate the lower dose, the subject will be withdrawn from the trial, In Part 2A, if a subject does not tolerate the dose of 20 mg M8891, the subject will be withdrawn from the trial (see Section 5.5). AEs assessed by the Investigator to be exclusively related to the

subject's underlying disease or medical condition/concomitant treatment are not applicable to the guidelines for dose modification.

The following dose modification guideline in Cycle 2 and subsequent cycles is recommended (Table 8).

Table 8 Recommendation to the Investigator for M8891 Dose Adjustment Based on Non-hematological Adverse Events

CTCAE v. 4.03 Grade	Guideline for Management	Dose Adjustment
1	No intervention	None
2	Treatment as appropriate according to PI's judgment	Dose reduction can be considered after discussion with the medical monitor or SMC decision.
≥ 3	Treatment as appropriate according to PI's judgment	Treatment held until Grade 1 after ≤14 days, then the subject may continue treatment at a lower dose i.e., 1 level below the current dose or defined by SMC.

PI: Principal Investigator.

Guidelines for the management of specific AEs are provided in Section 6.5.5.

In the case of M8891 dose modifications, the SMC might modify the SoA based on emergent data (e.g. PK sampling, if the dose must be adjusted).

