1	Add supportive care as indicated. Continue cabozantinib treatment at the current dose level if AE is manageable and tolerable.
2, tolerable and are easily managed)	Continue cabozantinib treatment at the current dose level with supportive care.
2, intolerable and cannot be adequately managed	At the discretion of the Investigator, cabozantinib should be dose reduced or interrupted ^b .
3 (except clinically non-relevant laboratory abnormalities)	Cabozantinib should be interrupted unless the toxicity can be easily managed with a dose reduction and optimal medical care ^b .
Grade 4 AEs (except clinically non-relevant laboratory abnormalities)	Subjects should have cabozantinib interrupted immediately. Discontinue cabozantinib unless the following criteria are met: 
• Subject is deriving clear clinical benefit as determined by the Investigator and agreed by the Sponsor• Toxicity can be managed with a dose reduction following recovery to Grade 1 (or baseline) and optimal medical care

AE: Adverse event.

^a Study treatment dose adjustment is only needed if the toxicity was deemed related to cabozantinib treatment or had an unclear relationship to cabozantinib treatment.

^b It is recommended that dose holds be as brief as possible.

Guidelines for the management of specific AEs are provided in Section 6.5.5.

5.1.3.5.3

Cabozantinib or M8891 Dose Reinstitution

If the subject recovers from his/ her toxicities to CTCAE version 4.03 Grade \leq 1 or to the baseline value (or lower) and the toxicity was unrelated to study treatment, then study treatment may be restarted with no change in dose.

If the subject recovers from his or her toxicities to Grade \leq 1 or to the baseline value (or lower) within 2 weeks and the AE was deemed possibly related to study treatment, then study treatment may be restarted at a reduced dose (see Section 5.1.3.5).

In case of dose reduction, re-escalation of cabozantinib or M8891 to the previous dose is not allowed.

5.1.4

Follow-up

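### After average QTcF above 500 ms without QT-caused symptoms, Table 12 and Section 5.1.3.5.3 give different restart instructions, and neither is said to prevail

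*Protocol*

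**What the plan says.** **Table 12, QTcF row (Protocol Section 6.5.5; Part 2).** The trigger is: "If at any time on study the average QTcF interval from the 3 ECGs is > 500 ms, the following actions should be taken". The first action is to withhold treatment. Then: "Study treatment may be restarted at a reduced dose level if ALL the following conditions are met". The conditions are that any symptoms are judged not to come from the QT prolongation, that QTcF is back to 500 ms or less, that "Study treatment has been interrupted through a minimum of 1 week following the return of the QTcF interval to ≤ 500 ms", that "QT prolongation can be unequivocally associated with an event other than study treatment administration and is treatable/has been resolved", and that the sponsor has reviewed the case and agrees. Permanent discontinuation has two triggers: symptoms confirmed as caused by the prolongation, or recurrence after a restart at a reduced dose.

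**Section 5.5.1.** The QTcF criterion for withdrawal from M8891 uses the same two triggers.

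**Section 5.1.3.5.3 (dose reinstitution, either drug).** After recovery to Grade 1 or less, or to baseline, if "the toxicity was unrelated to study treatment, then study treatment may be restarted with no change in dose". If recovery came within 2 weeks and "the AE was deemed possibly related to study treatment, then study treatment may be restarted at a reduced dose". A dose once reduced may not be raised again.

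**Two narrower statements.** Table 10 footnote a, for cabozantinib: "Study treatment dose adjustment is only needed if the toxicity was deemed related to cabozantinib treatment or had an unclear relationship to cabozantinib treatment". Section 5.1.3.5.1, for M8891, says that AEs judged to be due only to the "underlying disease or medical condition/concomitant treatment are not applicable to the guidelines for dose modification".

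**The concern.** In the general rules, relatedness to treatment is the reason to reduce the dose, and unrelated events are spared. In the QTcF row it works the other way: a reduced-dose restart is open only to events that are clearly not caused by treatment. A site with a recovered QTcF event can therefore find two different answers in the same protocol.

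Three things are at stake:

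- **Dose.** Because re-escalation is barred, a reduction made under Table 12 for an unrelated event is permanent. Under Section 5.1.3.5.3 it need not happen at all.
- **Restart or hold.** For a possibly related event without symptoms, one text permits resumption and the other does not.
- **Recurrence.** The permanent-stop trigger presupposes a reduced-dose restart. It does not reach a second episode in a subject who resumed at an unchanged dose.

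**Working it through.** No figure in the plan is at issue, so the check is to apply each text to each kind of subject.

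**Inputs.** Table 12 QTcF row and Section 5.5.1 (QTcF-specific); Section 5.1.3.5.3 (general, both drugs); Sections 5.1.3.5.1 and 5.1.3.5.2 (drug-specific). Section 7.4.1.1 reserves the unrelated category for events that are clearly not related. An event meeting Table 12's causality condition would therefore normally count as unrelated under Section 5.1.3.5.3.

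| Case (average QTcF > 500 ms) | Table 12 and 5.5.1 | 5.1.3.5.3 | Result |
|---|---|---|---|
| A. Unequivocally another cause; recovered to Grade 1 or less or baseline; other Table 12 conditions met | Restart at a reduced dose only | Restart with dose unchanged | Differ |
| B. Possibly related, no symptoms, first episode, recovered within 2 weeks | Causality condition fails, so no restart; neither permanent-stop trigger met | Restart at a reduced dose | Differ |
| C. Symptoms confirmed as QT-caused | Permanent discontinuation in both places | General text only; 5.5.1 is mandatory | Settled |
| D. Recurrence after a reduced-dose restart | Permanent discontinuation in both places | General text only; 5.5.1 is mandatory | Settled |
| E. Recurrence after an unchanged-dose restart made under 5.1.3.5.3 | New hold; permanent-stop wording not met unless symptoms are QT-caused | Depends again on causality | Gap |

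**Case A.** Only Section 5.1.3.5.3 contradicts Table 12 directly. Section 5.1.3.5.1 points the same way but covers M8891 and exclusively other causes. Table 10 footnote a covers cabozantinib and says when an adjustment is needed, which does not forbid one.

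**Case B.** The QTcF-specific text sets no end point for the hold. The general rules do supply some:

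- Section 5.1.3.5.2 ends cabozantinib after an AE interruption of more than 6 weeks.
- Table 8 ties continued M8891 after a Grade 3 or higher non-hematological event to recovery within 14 days, then a lower dose.
- Section 5.5.1 withdraws M8891 for a DLT.

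Whether the last two apply depends on the CTCAE grade of QTcF above 500 ms, which the documents do not give. The restart rules among these (Section 5.1.3.5.3 and Table 8) would allow what Table 12's causality condition excludes.

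**Precedence.** Sections 5.1.3.5.1 and 5.1.3.5.2 refer to Section 6.5.5 for specific AEs. Several rows of Table 12 refer back to Section 5.1.3.5. Section 5.1.3.5.3 makes no exception for QTcF, and no sentence ranks the two.

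**Number of subjects.** Part 2 plans at most 15 (Part 2A) + 40 (Part 2B) = 55 subjects. The documents give no rate of QTcF above 500 ms. Purely as an assumption, 1% to 5% would be 0.55 to 2.75 subjects at that maximum.

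**The case against.** The strongest reply is that Table 12 is the event-specific rule and so governs. Sections 5.1.3.5.1 and 5.1.3.5.2 send the reader to Section 6.5.5, the second of them directly before Section 5.1.3.5.3. The QTcF text in Section 5.5.1 points there too, and Section 7.4.5.2 names Table 12. Both texts are permissive, so a site that follows Table 12 breaches nothing in Section 5.1.3.5.3. Table 12 also requires immediate notice to the sponsor and its agreement before treatment continues, and its footnote calls for consultation on any dose modification. A unilateral full-dose restart is therefore unlikely. The recovery standards differ as well (Grade 1 or baseline against 500 ms or less held for a week), so the two texts do not always apply to the same subject at the same time.

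Much of this stands. It makes Table 12 the more natural rule to follow and reduces divergence between sites. It does not close the point. The protocol never says that Table 12 overrides Section 5.1.3.5.3, the table's own column is headed as a recommendation, and the sponsor, when asked to agree, has two texts to apply. The recurrence wording also remains narrower than the restarts that Section 5.1.3.5.3 allows.

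**Conclusion.** The inconsistency is real and confined to Part 2 subjects with average QTcF above 500 ms and no QT-caused symptoms. For them, Table 12 and Section 5.1.3.5.3 differ both when the event is unrelated and when it is possibly related. The recurrence stop does not cover an unchanged-dose restart. The number affected cannot be derived and is probably small. The case for acting rests on unreconciled safety instructions, not on frequency.

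A reader might infer more, and the documents do not support it:

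- *That a treatment-related, asymptomatic event has no stated outcome.* This is true of the QTcF-specific text only; general rules give outcomes.
- *That three statements contradict Table 12 equally.* Only Section 5.1.3.5.3 does so directly.
- *That every subject above 500 ms gets opposite instructions.* Each subject falls in one branch, and those with QT-caused symptoms are handled consistently.
- *That the RDE or RP2D would be affected.* No event rate is given, Section 3.3.1 reports no preclinical or preliminary clinical sign that M8891 prolongs QTcF, and the dose-modification tables are descriptive.

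**What to change.** Reconcile the QTcF row of Table 12 with Sections 5.1.3.5.1, 5.1.3.5.2 (Table 10 footnote a), 5.1.3.5.3 and 5.5.1, so that each of three cases has one consistent instruction: prolongation unrelated to treatment; related or unclear without symptoms; and QT-caused symptoms. For the second case, state how the hold ends. Add a sentence saying whether the Table 12 QTcF row or Section 5.1.3.5.3 takes precedence. Align the recurrence wording in Section 5.5.1 and Table 12 with whichever restarts the reconciled text allows. The clinical team decides the content; this review takes no view on which rule is right.

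The cost is protocol wording in one table row, a few sentences and a cross-reference. It adds no procedures, visits or subjects and changes no analysis.
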